4.1. **Include statistical power calculations and the assumptions made in making these calculations.** The following power calculations for Aims 1-3 assume the availability of 86 subjects who are eligible for randomization into one of two groups (n=43 per group). We assume a range of intra-class correlation of 0.1-0.5 and up to 10 follow-up measures per participant. The sample size is inflated to accommodate a 30% missing or dropout rate by 6 months based on rates over a similar period of time in previous studies⁵⁵. We consider a conservative adjustment in the two-sided level of significance, 0.025, to account for two hypothesis tests per Aim (3-month and 6-month outcome). Table 4 presents the detectable effect size based on the above assumptions for 90% and 80% power. The study will have 80% power to detect a moderate effect size of 0.50 standard deviations of a continuous outcome measure at 6 months assuming an intra-class correlation of 0.3. Table 5 presents the detectable effect in units applicable to each outcome based on the observed standard deviation from studies in the literature.

Power	Intra-class Correlation	Detectable effect size	
		3 months	6 months
80%	0.1	0.35	0.40
	0.3	0.48	0.50
	0.5	0.58	0.61
90%	0.1	0.40	0.41
	0.3	0.55	0.57
	0.5	0.66	0.70

(Assumptions: power=80%; n=30 per group after 30% attrition; 2-sided=0.05)

- Standard Deviation
- Insomnia Se
- Quality of Life
- Pooled within group standard deviation
- Pooled within group standard deviation (estimated from presented data)
- Pooled within group standard deviation for general health

Outcome	Pre-Post S.D. ^a	Detectable Difference
ISI ^b	3.809 ^d	1.90 points
Abstinent Days	15.96 ^e	7.98 %
Health Related QOL ^c	9.15 ^f	4.58 points

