model. In this model, the mean ISI depends on fixed covariates and random effects⁵⁷. The fixed covariates of interest include time, treatment assignment, the interaction between time and treatment assignment, adjusting for family history of alcoholism and confounding variables identified in the preliminary analysis. The random effects represent the unobserved factors that lead to variation of the individual participant's outcome. Random intercepts for each participant permit modeling of natural variation across participants at baseline in the outcome of interest. In addition, random slopes or random effects for the trajectory of each participant over time allow for variation of each participant about a mean, overall trajectory across all participants. Estimates of the random effect for an individual participant also permit far more focused investigations of those individuals who depart from the mean over time and experience either better or worse than average change in outcome. Thus, the mixed effects longitudinal model permits both comparisons of groups as well as contrasts of individuals. Although less robust to model misspecification, the mixed effects paradigm offers special flexibility in longitudinal data when exposures vary over time and when dropout and missed visits lead to unbalanced groups. ISI and quality of life are continuous measures and most likely follow a symmetric or approximately normal distribution. Therefore the linear mixed regression model is appropriate. If departures from normality are found, we will consider transformations or other distributional forms that may better fit the data. The alcoholism-related outcome measures are counts (e.g. number of days abstinent, number of heavy drinking days, etc.) but will be summarized as percentages (e.g. percent abstinent days) and will also most likely follow a normal distribution. The target of inference is the participant-specific response to treatment over time. Specifically we are interested in the efficacy at the end of treatment (8 weeks) and durability after 3 and 6 months of follow-up. At each time point of interest, we will estimate from the fitted model the difference from baseline in the outcome for each treatment group and test the difference between these differences. The treatment effects will be the contrasts that represent the difference of differences from baseline in outcome across treatment groups at 3 and 6 months. Both univariate and multivariate results will be reported in terms of Wald test, point estimates, and 95% confidence intervals.

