
Exploratory Aim 4: We will examine whether family history of alcoholism modifies the effect of the intervention on outcomes. Effect modification or moderators of the intervention will be tested and estimated with 3- and 2-way interactions among the treatment factor, potential moderator, and time in the ITT models described above. Because the hypotheses relating to effect modification will be exploratory, we will use $p=0.1$ to declare significance of such interactions. The analyses will be followed with stratified analyses corresponding to the effect modification hypotheses.

Regarding missing data and drop-out, we will assess the relationship of missing data patterns with dependent and independent variables. Specifically, we will use logistic regression with missingness as the binary outcome and dependent and independent variables under each Aim as covariates for the missing data model. If there are significant associations, we will perform multiple imputations with PROC MI in SAS, and take weighted averages of parameter estimates and standard errors from the longitudinal regressions across the multiple imputation iterations.

W. Privacy and Confidentiality

1. **Indicate the type of data that will be received by the Principal Investigator. Check all that apply.**

- 1.1. De-identified – Without any identifiers that could link the data to a specific participant. (Contact Privacy Officer for assistance. If data is coded, it is not considered de-identified.)

- 1.2. Identified – Linked to a specific participant by identifiers sufficient to identify participants. (See HIPAA and Common Rule Criteria for list of identifiers.)
- 1.3. Coded – Linked to a specific subject by a code rather than a direct identifier. If coded is checked, specify:

1.3.1 **Explain who will maintain the link or code.** The principal investigator and the research assistant will have access to the codes, which will be stored in a locked filing cabinet in room #228 or in the locked cabinet in [name] office (TBA). In addition, the code will also be stored in a back-up file in the password protected online drive of the principal investigator on the MIRECC drive (\\vhaphifpcmirecc\Research Studies\[name] – CBT-I) or the K: drive of the PI\vhaphiclunas11s (K:).

1.3.2 **Describe who will have access to the link or code.** P.I., and/or the study coordinator.

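### Section V.4.1 gives both 0.025 and 0.05 as the two-sided level, section V.4.2 gives none for Aims 1-3, and one Table 4 cell does not fit (minor)

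*Combined protocol and SAP*

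**What the plan says.** **Section V.4.1 (power).** The text sets the level: "We consider a conservative adjustment in the two-sided level of significance, 0.025, to account for two hypothesis tests per Aim (3-month and 6-month outcome"). It then says "Table 4 presents the detectable effect size based on the above assumptions for 90% and 80% power", and concludes: "The study will have 80% power to detect a moderate effect size of 0.50 standard deviations of a continuous outcome measure at 6 months", at an intra-class correlation (ICC) of 0.3. The assumptions line near Tables 4 and 5 gives 80% power and "n=30 per group after 30% attrition; 2-sided=0.05".

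**Section V.4.2 (analysis of Aims 1-3).** No significance level is given for these aims. Results are to be "reported in terms of Wald test, point estimates, and 95% confidence intervals". The only level in the section is for the exploratory effect-modification analysis: "we will use $p=0.1$ to declare significance of such interactions".

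**Time points in V.4.2.** The plan says: "Specifically we are interested in the efficacy at the end of treatment (8 weeks) and durability after 3 and 6 months of follow-up". At each of these it will estimate "the difference from baseline in the outcome for each treatment group and test the difference between these differences". It then defines the treatment effects as the 3- and 6-month contrasts only.

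**The concern.** Two levels are printed in one section, and the section that governs the analysis does not choose between them. The 0.025 appears only in the power calculation. An analyst working from V.4.2 alone would find Wald tests, 95% intervals and no threshold. For each aim's main contrasts, a p-value between 0.025 and 0.05 could then be declared significant or not, depending on which line is followed.

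Two smaller gaps go with this. A between-group test at week 8 is planned but has no stated role, and the two-test count in V.4.1 does not include it. One Table 4 entry also disagrees with its neighbour.

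**Working it through.** **Inputs, all from V.4.1.** 43 per group; 30% attrition; ICC 0.1 to 0.5; up to 10 follow-up measures; the 12 cells of Table 4; the Table 5 standard deviations 3.809, 15.96 and 9.15.

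**1. The plan's own figures.**
- Attrition: 43 x 0.70 = 30.1, which gives the stated 30 per group.
- Table 5: 0.50 x 3.809 = 1.905; 0.50 x 15.96 = 7.98; 0.50 x 9.15 = 4.575. The printed values are 1.90, 7.98 and 4.58. Table 5 is therefore 0.50 SD throughout, which is the Table 4 cell for 80% power, ICC 0.3, 6 months.
- Direct check of that cell: d = (z_alpha/2 + z_power) x sqrt(2(1 + (m-1) x ICC)/(m x n)). Take n = 30, ICC 0.3 and m = 10 to 8 measures (m is an assumption; the plan gives only a maximum). At 0.025, d = 0.484 to 0.496. At 0.05, d = 0.440 to 0.450. The printed 0.50 fits 0.025 better.

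**2. Which level produced Table 4.** The ratio of the 90%-power effect to the 80%-power effect does not depend on n, m or ICC:

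(z_alpha/2 + 1.282)/(z_alpha/2 + 0.842) = 1.143 at 0.025 (z = 2.241) and 1.157 at 0.05 (z = 1.960).

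| Visit, ICC | 90% / 80% | Ratio |
|---|---|---|
| 3 months, 0.1 | 0.40 / 0.35 | 1.143 |
| 3 months, 0.3 | 0.55 / 0.48 | 1.146 |
| 3 months, 0.5 | 0.66 / 0.58 | 1.138 |
| 6 months, 0.3 | 0.57 / 0.50 | 1.140 |
| 6 months, 0.5 | 0.70 / 0.61 | 1.148 |
| 6 months, 0.1 | 0.41 / 0.40 | 1.025 |

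The first five pairs pool to 2.88/2.52 = 1.143, the value for 0.025. Allowing for rounding, 0.66/0.58 is at most 0.665/0.575 = 1.1565. That falls just short of the 1.1570 needed for 0.05. The other four pairs alone do not separate the two levels.

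**3. Table 5 if 0.05 per test had been used.** 0.50 x (1.960 + 0.842)/(2.241 + 0.842) = 0.454 SD, or 1.73 points, 7.25% and 4.16 points. The printed values are not these.

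**4. The cell that does not fit.** With rounding, 0.41/0.40 is at most 0.415/0.395 = 1.051. That would need z_alpha/2 of about 7.8 or more, which no usual level gives. If 0.41 is right, the 80% cell is 0.41/1.1427 = 0.359 (0.354 to 0.363 with rounding).

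**5. Error per aim.** This treats the visit contrasts as distinct, equally correlated normal statistics. The correlations are assumed, since the plan gives none.

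| Tests | 0 | 0.5 | 0.8 | 0.9 |
|---|---|---|---|---|
| Two at 0.025 | 4.9% | 4.7% | 4.0% | 3.6% |
| Two at 0.05 | 9.8% | 9.1% | 7.8% | 7.0% |
| Three at 0.025 (week 8 also claimed) | 7.3% | 6.6% | 5.2% | 4.4% |

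**The case against.** The case for leaving the plan alone is fairly strong. The 0.025 is set out in a full sentence with its reason. The 0.05 sits in a parenthetical list of power inputs, in a part of the text where table captions and footnotes are damaged, so its attachment to Table 5 is an inference. It may also mean the total per aim, since 2 x 0.025 = 0.05. All of that stands. It makes a labelling slip the likeliest explanation, but the line does not say per aim, and V.4.2 does not resolve the question.

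Three stronger readings are tempting, and the documents do not support them.

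- **That the plan tests at 0.05 each and so has a 9-10% error per aim.** The 95% intervals do not establish this, because they are general reporting and are often shown beside an adjusted test level. The figure of 9-10% also holds only for correlations up to about 0.5. If time enters the model as a linear term, the visit contrasts are multiples of one coefficient, their Wald tests coincide and there is no multiplicity. V.4.2 mentions random slopes and does not say whether time is categorical.
- **That week 8 is a third, uncontrolled confirmatory test.** The two-test count in V.4.1 and the treatment-effect definition in V.4.2 both point to 3 and 6 months. Even if week 8 were claimed at 0.025, the error would be below 5% at correlation 0.9. It would be equally wrong to declare week 8 secondary on the sponsor's behalf, because V.4.2 ties efficacy to week 8 and durability to the later visits.
- **That the sample size or power is wrong.** The figures follow 0.025, and the 0.40 cell overstates the detectable effect, which is the conservative direction. With n = 30 and 8 to 10 measures, the formula in the working does not match every cell exactly: it gives 0.590 to 0.597 at ICC 0.5, 80% power, against 0.61 at 6 months. The plan does not state its formula or the effective n and m per visit, so this is not evidence of an error.

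**Conclusion.** The concern holds as a minor inconsistency in a decision rule. Two levels are printed, the tables follow 0.025, and the analysis section is silent for Aims 1-3. If the looser level were applied to each of two distinct contrasts, the per-aim error would be about 7-10% instead of below 5%. That range assumes categorical time and correlations from 0.9 down to 0.

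The role of week 8 is unstated; that is a missing label, not a demonstrated loss of error control.

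The 0.40 cell in Table 4 is inconsistent with 0.41 under any usual level. This conclusion uses only the ratio and needs no assumption about n, m or ICC. The replacement of about 0.36 does assume that 0.41 is the correct member of the pair. The cell does not feed Table 5.

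**What to change.** 1. In V.4.1, correct the assumptions line to two-sided 0.025 per test (0.05 per aim).
2. In V.4.2, state that for each of Aims 1-3 the 3- and 6-month contrasts are tested at two-sided 0.025 each. The 95% intervals may stay if the text says that significance is judged at 0.025. Matching 97.5% intervals are optional and would be about 14% wider (2.241/1.960 = 1.144).
3. Have the sponsor state whether the week-8 contrast is outside this family, as the two-test count and the treatment-effect definition imply, or inside it. If inside, the split must cover three tests, for example 0.05/3 = 0.0167 each. Power for 0.50 SD at ICC 0.3 would then be about 76% to 79% (n = 30 with 8 to 10 measures, against 81% to 83% at 0.025).
4. Recompute the Table 4 cell for 80% power, ICC 0.1, 6 months.

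The cost is one corrected line, one or two sentences and one table cell. N=86, the 0.50 SD statement and the Table 5 values need no change. Only bringing week 8 into the family would cost power.

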- 4.2. **Define plans for data and statistical analysis, including key elements of the statistical plan, stopping rules and endpoints.** *Overview:* Our study proposes a longitudinal repeated-measures parallel-group design. This powerful design, with a baseline measurement and up to ten follow-up measures per participant over 6 months, allows for comparisons within each participant over time as well as across participants (treatment groups). The main analysis will look at differences between intervention groups in the changes in outcomes over time (i.e. insomnia severity, alcoholism-related outcomes and daily functioning). *Randomization:* Patients will be recruited and randomized as individuals. Allocation will be uniform across the two groups after suitable blocking and stratification on family history of alcoholism to ensure optimal balance of participant characteristics and to observe relationships between groups with and without a family history of alcoholism in the Exploratory Aim. Participants are randomly assigned to the CBT-I group, or the QDT group. The study biostatistician will create randomization sequences by family history of alcoholism (separate sequences) using a pseudo-random number generator with block sizes of 4. Two boxes of sequentially numbered, sealed, opaque envelopes will be prepared using the randomization sequences and labeled "Family History" and "No Family History". At the time of randomization, the first envelope, in sequential order, is pulled from the appropriate box and opened to reveal the group assignment. All the staff conducting assessments will be blinded to the allocation of treatment arm with the exception of [name], the BSM treatment provider, [name] the person overseeing treatment allocation, and [name], the monitor for BSM treatment for the study. *Preliminary Analyses:* All data, regardless of the format, will first be assessed by [name] and his mentors for missing data, distributions of all observed measures, and out-of-range values by means of conventional descriptive tables. SAS v9.3 will be our primary tool for these analyses as the software is both mature and well-documented⁵⁶. Next, we will employ raw and smoothed plots to visualize the individual and average trajectories of all repeated measures over time according to assigned treatment and by participant characteristics. All questions of data quality and integrity will be investigated before any statistical modeling, since complete and accurate data are essential for unbiased estimates and confidence intervals. We will compare all baseline variables across groups to check the adequacy of randomization. The baseline comparisons will be based on: 1) t-test or Wilcoxon rank sum tests for continuous variables depending on the symmetry of the distributions; 2) on logistic regression for binary or ordinal variables; and 3) on Poisson log-linear regression for count data. If imbalances are found at baseline, then the relevant variables will be treated as confounders in the analysis.

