
Specific Aims 1-3: The analysis for the specific aims 1-3 is based upon the intent-to-treat principle; all randomized participants will be included in the analysis regardless of whether they drop out of the intervention or study. The analysis will involve the comparison of the insomnia severity (Aim 1), abstinence from drinking (Aim 2), and quality of life (Aim 3) across the intervention groups in order to allow for different trajectories of the outcome measures and to afford flexibility in making contrasts within participants over time and across participants while simultaneously controlling for potential confounding factors, we propose the participant-specific or *mixed effects* linear

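### The stated 80% power for 0.50 SD at 6 months fits a comparison averaged over follow-up visits, not the 6-month change-from-baseline contrast that the plan tests, and should be restated

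*Combined protocol and SAP*

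**What the plan says.** Section V.4.1 assumes 86 randomised participants (43 per arm), 30% loss by 6 months, an ICC between 0.1 and 0.5, and up to ten follow-up measures. It sets two-sided 0.025 "to account for two hypothesis tests per Aim (3-month and 6-month outcome"). On that basis it states: "The study will have 80% power to detect a moderate effect size of 0.50 standard deviations of a continuous outcome measure at 6 months", at ICC 0.3. Table 4 lists detectable effects at 3 and 6 months. Table 5 turns 0.50 into outcome units using a column headed Pre-Post S.D. An assumptions line that appears to belong to Table 5 reads "Assumptions: power=80%; n=30 per group after 30% attrition; 2-sided=0.05".

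Section V.4.2 describes the analysis: "The main analysis will look at differences between intervention groups in the changes in outcomes over time". The treatment effects are "the contrasts that represent the difference of differences from baseline in outcome across treatment groups at 3 and 6 months", taken from a mixed model with time, treatment, their interaction, random intercepts and "random slopes or random effects for the trajectory of each participant over time". It adds that "we are interested in the efficacy at the end of treatment (8 weeks) and durability after 3 and 6 months of follow-up". It does not say whether time is categorical, linear or another form, or whether baseline means are held equal between arms.

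**The concern.** The number of follow-up measures and the ICC enter a power calculation in this way when repeated visits are averaged. Averaging many visits removes much of the within-person noise. A contrast at one named time gets that benefit only as far as the model's time form borrows information from other visits. The power statement and the planned test may therefore describe different comparisons.

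The 6-month contrast carries the durability claim in Hypothesis 1 under the primary aim. A reader of a null 6-month result would credit the trial with an 80% chance of detecting 0.50 SD, printed as 1.90 points on the Insomnia Severity Index (ISI).

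**Working it through.** **Inputs.** From section V.4.1: 30 per arm after attrition (43 × 0.7 = 30.1), ICC 0.3, two-sided 0.025, effect 0.50 SD. The normal multipliers are 2.241 for alpha, 2.241 + 0.842 = 3.083 for 80% power and 2.241 + 1.282 = 3.523 for 90%. Assumed here: visits at weeks 0–8, 21 and 34, every outcome measured at every visit, and equal correlation between visits.

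**1. Reproducing Table 4.** For the average of m equally correlated follow-ups with n per arm, the detectable effect is multiplier × √[2(1 + (m − 1)·ICC)/(m·n)].

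| Column | n, m | Power | Formula, ICC 0.1/0.3/0.5 | Printed |
|---|---|---|---|---|
| 3 months | 31, 9 | 80% | 0.350/0.481/0.584 | 0.35/0.48/0.58 |
| 3 months | 31, 9 | 90% | 0.400/0.550/0.667 | 0.40/0.55/0.66 |
| 6 months | 28, 10 | 80% | 0.359/0.501/0.611 | 0.40/0.50/0.61 |
| 6 months | 28, 10 | 90% | 0.410/0.573/0.698 | 0.41/0.57/0.70 |

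Eleven of 12 cells agree within 0.01. These n and m were chosen to fit. With n = 30 and m = 9, untuned, 11 of 12 agree within 0.025. Power for 0.50 SD at n = 30 is then 81.8% (m = 9) or 82.7% (m = 10). At alpha 0.05 the same formula gives about 88–89%, so 0.025 lies behind the printed figure.

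**2. The planned 6-month contrast.** Power = Φ(δ/SE − 2.241). δ is 0.50 if the unit is the outcome SD. If the unit is the SD of change, which is √[2(1 − 0.3)] = 1.183 outcome SDs, δ is 0.50 × 1.183 = 0.592.

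- Categorical time: SE = √1.4 × √(2/30) = 0.3055.
- Categorical, baseline-adjusted: SE = √(1 − 0.3²) × √(2/30) = 0.2463.
- Linear time, random intercept only: SE = 34 × √[1.4/(30 × 1048.2)] = 0.2269, where 1048.2 is the sum of squared deviations of the 11 visit weeks.
- Linear time, common baseline: SE = 0.2138 by generalised least squares.

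| Form | Power, outcome SD | Power, change SD | 80% detectable, outcome SD | 80% detectable, change SD |
|---|---|---|---|---|
| Categorical | 27% | 38% | 0.94 | 0.80 |
| Categorical, baseline-adjusted | 42% | 56% | 0.76 | 0.64 |
| Linear | 49% | 64% | 0.70 | 0.59 |
| Linear, common baseline | 54% | 70% | 0.66 | 0.56 |

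Piecewise time with a knot at week 8 is close to linear: 47.5/54% (own/common baseline) in outcome SD and 63/70% in change SD. With follow-up at weeks 13 and 26, the two linear figures fall to 43/49% and 58/65%.

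**3. Forms that do better** (own/common baseline):

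- Effect rising to week 8 and then held: 67/85% in outcome SD, 83/95% in change SD.
- Constant effect at every post-baseline visit: 49/92% in outcome SD, 64/98% in change SD.
- Ramp to week 8 plus one separate follow-up level: 59/70% in outcome SD, 75/85% in change SD.
- Log time: 43/65% in outcome SD, 58/80% in change SD.

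**4. In ISI points.** Table 5 prints 0.50 × 3.809 = 1.90. Using the detectable effects in step 2, the values are 3.0/2.4/2.3/2.1 points if 3.809 is an SD of change, or 3.6/2.9/2.7/2.5 if it is a single-visit SD.

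**5. The 0.40 cell.** At alpha 0.025 the 90% to 80% ratio must be 3.523/3.083 = 1.143. Five printed pairs give 1.138–1.148. The 6-month pair at ICC 0.1 gives 0.41/0.40 = 1.025, whereas 0.41/1.143 = 0.36.

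**The case against.** The strongest reply is that the plan fixes no time form, so categorical and linear time are no more stated than the forms that reach 80%. That is correct, and it rules out a single replacement figure. But the held, constant and single-follow-up-level forms make the 3- and 6-month contrasts identical, although section V.4.1 adjusts alpha for two tests. Log time reaches 80% only with both a common baseline and change-SD units.

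A reader might infer from Table 4 that the calculation ignored baseline altogether, because its detectable effect rises with ICC while that of a visit-specific change falls (1.07/0.94/0.80 at ICC 0.1/0.3/0.5). The documents do not support this. The fall occurs only in outcome SD; in change SD the figure is 0.80 at every ICC. If the ICC were defined among change scores, the averaging formula would fit Table 4 equally well. What is shown is averaging over visits as against a contrast at one time.

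A reader might also take 27% as the true power. It is the least favourable form. The wording on individual trajectories leans towards continuous time, where the gap is smaller. Section V.4.2 also says "all randomized participants will be included in the analysis regardless of whether they drop out of the intervention or study". If all 43 per arm contribute and retention falls steadily by week to 70% at week 34 (an assumption), linear time gives 52/57% in outcome SD and 68/73% in change SD. Linear time passes 80% only in change SD with no dropout (81/86%), which sets aside the plan's own attrition. The plan's random slopes work the other way. With an assumed slope variance at 6 months of 0.10 or 0.25 SD², linear time in outcome SD falls to 43–48% or 37–41%.

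Two smaller replies stand in part. The SD unit is named, but inconsistently: outcome measure in the text, pre-post in Table 5. And 0.05 may be the overall level with 0.025 per test, in which case the line needs only a label; Table 5's layout is broken in the text available, so its placement is inferred.

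**Conclusion.** The point holds in this form: the 80% fits an average over follow-up visits and is not delivered by the 6-month difference in change under categorical, linear or piecewise time. Across those forms, with 30 per arm, ICC 0.3 and two-sided 0.025, power runs from 27% to 54% in outcome SD and from 38% to 70% in change SD. The averaging formula is inferred from the fit, because the plan names none. The linear and piecewise figures rest on the assumed visit weeks and leave out random slopes.

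The finding is limited to 6 months. Under linear time, 0.50 SD at 3 months would imply 0.50 × 34/21 = 0.81 SD at 6 months, so the 3-month column needs its own calculation. The point does not show that the trial must enrol more or that its analysis is invalid, and the planned 95% intervals will show the real precision. The design statement should still be corrected, because a null durability result would be read against it.

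**What to change.** In section V.4.1, state the time form, the baseline handling, the n (30 completers, or 43 with partial data) and the SD unit of the planned contrast. Then recompute the power sentence and Tables 4 and 5 for that contrast at two-sided 0.025. Suggested wording: *With [n] per group, [time form], baseline [adjusted / not adjusted], ICC 0.3 and two-sided 0.025, the study has 80% power for [x] SD of [the outcome / change] at 6 months.* For 30 per group in outcome SD, x is about 0.94 (categorical), 0.76 (baseline-adjusted) or 0.70 (linear, random intercept only). Say whether 0.05 in the assumptions line is the overall level, and correct the 0.40 cell.

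The cost is rewording one section and two tables, and a less favourable stated detectable effect.
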